In this study participants are randomized into two groups: a structured exercise intervention group and a usual care control group. It is expected that there will be two levels of fatigue measurements: at baseline and after the exercise intervention. Our sample size calculation is based on analysis of covariance (ANCOVA) comparing mean fatigue score differences between the two intervention arms at the end of intervention, adjusting for baseline. In our exercise intervention study ([name] et al, unpublished data, mean fatigue scores of 42.53 (SD=9.35) and 37.12 (SD=9.42) were reported for the intervention and control arms, respectively. In the same study, the correlation coefficient between baseline and after intervention fatigue scores was calculated as 0.64. With the above guidelines and a level of significance of $\alpha=0.05$ (two-sided), we will use randomize 40 women/arm to obtain statistical significance between the arms with 90% power for the overall ANCOVA F-ratio.

Statistical analysis

Baseline characteristics will be compared between the two intervention groups using two-sample t-test or Wilcoxon rank-sum test depending on whether the t-test assumptions are satisfied or not. Suitably transformed variables will be used when necessary. Categorical variables will be compared between the two groups using chi-square tests or Fisher's exact test. The major analytical tool for addressing the specific aims of this study is linear mixed modeling for repeated measures. Study endpoints will be measured three times in each participant in the study, and it is expected that measures on the same individual will be correlated. We will also examine whether the variance of repeated measures changes over time. An appropriate correlation structure will be selected depending on whether there is a trend of variance with time or not. For each outcome measure of interest, a linear mixed repeated measures model will be fit to evaluate the main effects of time, study group, and group-by-time interaction. Known confounders and other covariates will be included in the linear mixed models if their individual bivariate associations with both the group variable and outcome are significant at 10% level.

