We hypothesize that participants in the intervention group will have lower average fatigue scores compared to the usual care group after the intervention. For Aim 1 and Aim 3, "change scores" will be defined as the difference between baseline score and 4 week, (end of radiation treatment) score. Change scores will be compared between the two groups using t-test or Wilcoxon rank-sum test. An ANCOVA model will be utilized to assess group differences in change scores adjusting for covariates including age. We hypothesize that participants in the structured exercise intervention group will have lower levels of fatigue (Aim 1) and lower levels of inflammatory biomarkers (Aim 3) compared to baseline at follow-up visits as compared to the usual care control group. We hypothesize that there will be at least partial normalization of both the fatigue levels reported and the inflammatory biomarkers to baseline by the 4-week follow-up visit. Linear mixed models as described above will be used to compare fatigue scores and inflammatory biomarkers levels over time across the study groups. For Aim 2, we will report rates of acceptability and adherence at baseline and end of intervention. We will use the binomial test to compare acceptance and adherence rates between the two intervention arms. Baseline and end of intervention acceptability levels evaluated using the Wilcoxon sign-rank test or McNemar's test (or generalized McNemar's test) for numerical and categorized outcomes, respectively.

A Graduate Research Assistant (GRA) will assist with data collection for the survey data. The GRA will collect log data of the women exercising using the Pedlar device. There is an hourly reimbursement for GRA labor without incentive. This has been approved via the Development Grant.

f. Significance

This study will contribute to the literature on the role of concurrent radiation treatment and moderate-intensity exercise in reducing cancer-related fatigue and improving HRQOL among breast cancer patients undergoing.

This study will also provide pilot data on the correlation of inflammatory markers with exercise-related changes in fatigue and other HRQOL measures in breast cancer patients undergoing RT. The strengths of this study include the use of an “in-office” easy to use exercise intervention that reduces participant burden, the timing of exercise inception that coincides with RT inception, and use of biomarkers.

g. Future Plans

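### No primary Aim 1 test is designated, and no listed analysis names the baseline-adjusted ANCOVA on which the 90% power rests

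*Combined protocol and SAP*

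**What the plan says.** **Sample size Considerations.** The calculation is for an "analysis of covariance (ANCOVA) comparing mean fatigue score differences between the two intervention arms at the end of intervention, adjusting for baseline". The inputs come from the team's own unpublished exercise study: means of 42.53 and 37.12, SDs of 9.35 and 9.42, and a baseline-to-post correlation of 0.64. The conclusion is that "we will use randomize 40 women/arm to obtain statistical significance between the arms with 90% power for the overall ANCOVA F-ratio", at two-sided 0.05.

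**Statistical analysis.** For Aim 1 the section offers:

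- An unadjusted comparison of change from baseline to 4 weeks: "Change scores will be compared between the two groups using t-test or Wilcoxon rank-sum test".
- An ANCOVA of the same change: "An ANCOVA model will be utilized to assess group differences in change scores adjusting for covariates including age".
- A mixed model over all three visits. It is introduced with "The major analytical tool for addressing the specific aims of this study is linear mixed modeling for repeated measures", and for each outcome "a linear mixed repeated measures model will be fit to evaluate the main effects of time, study group, and group-by-time interaction".

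The hypothesis for Aims 1 and 3 is that the exercise arm will have lower levels "compared to baseline at follow-up visits as compared to the usual care control group". No analysis is called primary, and baseline fatigue is not named as a covariate in any of them.

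**The concern.** The 90% power belongs to a model that uses the 0.64 correlation through a baseline covariate. A t-test or Wilcoxon test on change has no such covariate. The change-score ANCOVA has it only if the reader supplies it. The mixed model has three terms and two follow-up visits. The wording of the hypothesis points to the group-by-time term, but does not say whether that means the 4-week contrast or the joint two-degree-of-freedom test over both visits.

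Two things are at stake. First, Aim 1 is worded as a test of efficacy, and its power is not secured if the analysis actually run is one of the tests as written. Second, these tests are not equivalent. With no primary named in advance, the reported conclusion can depend on which one is quoted.

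**Working it through.** **Inputs (Sample size Considerations).** Difference 42.53 − 37.12 = 5.41. Pooled SD = √((9.35² + 9.42²)/2) = 9.385. Correlation ρ = 0.64; n = 40 per arm; two-sided α = 0.05. Unless stated otherwise, power is from the noncentral t with noncentrality 5.41/(SD × √(2/n)) and complete data.

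**1. The plan's own figure.** For the ANCOVA with baseline as covariate, the residual SD is 9.385 × √(1 − 0.64²) = 7.211. The noncentrality at 40 per arm is 5.41/(7.211 × √(2/40)) = 3.355 on 77 df, so power is **91.2%**. At 39 per arm it is 90.5% and at 38 it is 89.7%. Adding age costs one df and leaves 91.2%. The stated 90% reproduces.

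**2. Change-score t-test.** The documents give no baseline SD, so equal baseline and post SDs are assumed first. The SD of change is 9.385 × √(2 × (1 − 0.64)) = 7.963. The noncentrality is 3.038 on 78 df, so power is **85.1%**. For 90%, 46 per arm is just short (89.7%) and 47 is enough (90.3%). The Wilcoxon test on change has 83.0% (simulated, 20,000 trials).

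With k the assumed ratio of baseline SD to post SD, the SD of change is 9.385 × √(1 + k² − 2 × 0.64 × k):

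| k | SD of change | Power, 40 per arm |
|---|---|---|
| 0.8 | 7.366 | 90.0% |
| 0.9 | 7.613 | 88.1% |
| 1.0 | 7.963 | 85.1% |
| 1.1 | 8.405 | 81.1% |
| 1.2 | 8.923 | 76.4% |

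**3. Change-score ANCOVA with age only (equal SDs, 77 df).** If age explains 0, 5, 10 or 15% of the variance of change, power is 85.1, 86.8, 88.5 or 90.2%. Age would have to explain about 15% to recover 90%. With baseline in the model, the arm test is the same as in step 1.

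**4. Mixed model (assumed compound symmetry, ρ = 0.64, 156 df).** The 4-week-minus-baseline contrast between arms again has SD 7.963, and its power is 85.5%. For the joint group-by-time test, λ = (40/2) × (sum of squared deviations of 0, d1, d2 about their mean)/(9.385² × 0.36), where d1 and d2 are the arm differences at 4 weeks and at the follow-up visit. With d1 = 5.41:

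- d2 equal to zero or to d1: λ = 12.31, power 88.5%.
- d2 equal to half of d1: λ = 9.23, power 77.3%.

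**5. Do the tests agree?** In 20,000 trials simulated at the design effect with equal SDs, the change-score t-test and the baseline-adjusted ANCOVA fell on opposite sides of p = 0.05 in 8.2%. Under no effect (10,000 trials, same correlation), at least one of the change-score t-test, the baseline-adjusted ANCOVA and the joint interaction test reached p < 0.05 in about 9.6%.

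**The case against.** The strongest reply is that the two sections describe one analysis. The covariate list in the change-score ANCOVA is open-ended, the sample size section has already committed to baseline adjustment, and an ANCOVA of change with baseline included gives the same arm test as an ANCOVA of the final score. That reading is plausible, and on it the ANCOVA is under-specified rather than absent. But the text names age and leaves out the one covariate on which the power depends. The only written rule for adding covariates, given for the mixed models, requires an association with both group and outcome at the 10% level. Under randomisation, baseline fatigue would meet the group half of that rule in only about 10% of trials.

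A second reply is that the mixed model is the designated main tool, and that the 4-week time point is fixed for the change scores. Both are partly true. If the mixed model is primary, however, the primary test is not the powered one, and its contrast is still open.

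Other limits stand. The loss is moderate, and it vanishes at an SD ratio of 0.8. Most of the discordance restates the power gap: a simulation of 400,000 trials gave 8.4%, of which 7.1% was significant by ANCOVA only and 1.3% by t-test only. That simulation, which allows for chance baseline imbalance, puts the ANCOVA's power at 90.8% rather than 91.2%, and at 90.05% with 39 per arm. The study also describes its evidence as preliminary. That tempers the point, but a stated alpha and 90% power are still a commitment for Aim 1.

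**Conclusion.** The concern holds. The sample size is sound for the test it was calculated for, but the analysis section does not commit to that test. As written, the t-test on change and the age-only ANCOVA have about 85% power, the Wilcoxon test about 83%, and the joint mixed-model test about 77% to 89%. The ANCOVA behind the sample size has about 91%. The lower figures assume equal baseline and post SDs; the mixed-model range also assumes compound symmetry and a follow-up effect that the documents do not give. The lack of a designated primary test does not rest on any of these assumptions. This should be fixed before the data are analysed.

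**What to change.** Name one primary Aim 1 analysis: ANCOVA of 4-week FACIT-Fatigue (or, equivalently, of change from baseline) with baseline FACIT-Fatigue as an explicit covariate, testing the arm term at two-sided 0.05. Age can stay in the model as planned. Label the unadjusted change-score tests and the mixed model as supportive. State that the mixed model reports the arm difference at 4 weeks adjusted for baseline, and say how: baseline as a covariate, or a common baseline mean across arms. If the change-score t-test is kept as primary instead, restate its power as about 85% under equal SDs.

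The cost is wording only. Table 1 already schedules FACIT-Fatigue at baseline and at 4 weeks, and no patients or visits are added. The restored power of about 91% is for complete data. No dropout allowance is stated, and assumed losses of 5, 10, 15 and 20% (38, 36, 34 and 32 per arm) would give 89.7, 88.1, 86.2 and 84.0%.

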TITLE: A Randomized Controlled Trial of Exercise to Reduce Cancer Related Fatigue in Women Undergoing Radiation Treatment for Breast Cancer

PROTOCOL #: Pro2016-XXXX

STUDY DRUG: N/A

IND #: N/A

SPONSOR: Hackensack University Medical Center

PRINCIPAL INVESTIGATOR: [name].
Lombardi Comprehensive Cancer Center
[name]., Ph.D.
Hackensack University Medical Center

ORIGINAL

PROTOCOL VERSION: Version 1.0 – 15 Feb 2016

A Randomized Controlled Trial of Exercise to Reduce Cancer Related Fatigue in Women Undergoing Radiation Treatment for Breast Cancer

[name]., Ph.D. (HUMC)
[name]. (HUMC)
[name]. (HUMC)
[name]. (HUMC)
[name]. (HUMC)

[name]. (LCCC)
[name]. (LCCC)
[name]., Ph.D. (LCCC)

b. ABSTRACT

Cancer related fatigue (CRF) is a common and debilitating side effect of radiotherapy in breast cancer patients. Physical activity interventions can attenuate CRF. The proposed study is a randomized, controlled trial (RCT) of exercise of structured moderate-intensity exercise intervention, delivered concurrently with radiotherapy, to reduce CRF and improve health-related quality of life among breast cancer patients. Eighty women with breast cancer scheduled to receive radiation therapy at HUMC will be randomized to one of the two trial arms: 1) a facility-based aerobic exercise utilizing a portable stationary pedal exerciser; or 2) a control group. Intervention arm participants will exercise at the hospital either before or after their radiation treatment. Assessments will be conducted at baseline, 4 weeks into radiation course, and at 4-week follow-up visit. The outcome variables are CRF, biomarkers of inflammation, and health-related quality of life. The study will provide preliminary evidence on whether a short-term moderate-intensity exercise intervention might be effective in reducing CRF in women undergoing radiotherapy for breast cancer, and whether this effect is mediated by inflammation.

c. Specific Aims

The specific aims of this study are: (1) to test the efficacy of a structured, moderate intensity exercise intervention delivered concurrently with radiation therapy (RT) in reducing CRF among breast cancer patients; (2) to provide pilot data on the acceptability and adherence of the exercise intervention on women receiving treatment; and (3) to determine the impact of exercise on serum inflammation markers among women undergoing RT.

d. Background

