Participants will be randomly assigned to structured moderate-intensity aerobic exercise program or to the control group using a block randomization scheme. The study biostatistician ([name].) will generate the computer-based randomization sequence. The intervention assignment is placed in opaque envelopes and delivered to the study coordinator. After completing baseline assessments, eligible participants will be assigned to study arm by a study coordinator who will open the next one of the sequentially-numbered, sealed envelopes.

Intervention

Arm 1: Exercise Intervention Arm

Participants randomized to the exercise intervention will be required to exercise before or after each radiation treatment session, on a five-treatment per week schedule. No special accomodations will be made to open the clinic on weather days or on extra days in the event of machine failure or patient unavailability. The exercise intervention will be administered at the radiation treatment facility in a room allocated for the study. The exercise prescription consists of aerobic training utilizing the portable stationary pedal exerciser (Pedlar) which contains two cycling pedals mounted to a stationary block that allows patients to exercise while sitting. Pedal tension is adjusted to provide desired resistance. Exercise intensity is self-rated by participants, instructed that moderate intensity goal will "make you breathe somewhat harder than normal". Participants may move and position the device to permit comfortable use while sitting in a chair. Participants are required to perform 15 minutes/day of aerobic exercise using the Pedlar device on radiation treatment days; during a standard radiation course, this will typically yield 75 minutes/week of aerobic time. Ten Pedlar devices have been approved for purchase for HUMC Department of Radiation Oncology through the Development Grant. Participants will record their activity on a daily basis on an exercise log (Appendix H).

Arm 2: Control Arm

Control group participants will be told to maintain their current daily activities and exercise habits for the duration of their treatment.

Study retention and adherence

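### Aim 2's between-arm adherence test has no defined control value and cannot show whether women complete the exercise; report an exercise-arm proportion with an exact confidence interval instead

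*Combined protocol and SAP*

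**What the plan says.** The second of the Specific Aims is "to provide pilot data on the acceptability and adherence of the exercise intervention on women receiving treatment". For this aim the Statistical analysis section makes two statements. The first is descriptive: "we will report rates of acceptability and adherence at baseline and end of intervention". The second is inferential: "We will use the binomial test to compare acceptance and adherence rates between the two intervention arms". Since the trial has one exercise arm and one control arm, the second can only mean exercise against control.

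The exercise requirement stands under Arm 1: "Participants randomized to the exercise intervention will be required to exercise before or after each radiation treatment session, on a five-treatment per week schedule", and "Participants are required to perform 15 minutes/day of aerobic exercise using the Pedlar device on radiation treatment days". The daily exercise log is described in that same paragraph. Under Arm 2, controls are only told to carry on with their usual activity. The section on study retention and adherence says that adherence is taken from daily logs, which hold the woman's identification, the date and the time spent on the Pedlar.

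On timing, the Randomization section says "After completing baseline assessments, eligible participants will be assigned to study arm by a study coordinator". For Aims 1 and 3 the change score is the "difference between baseline score and 4 week, (end of radiation treatment) score".

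**The concern.** Aim 2 is a question about one arm: do women on radiotherapy accept the exercise and complete it? A comparison with women who were assigned no exercise does not address that, and it needs a control value that the visible text does not supply. Whoever runs the analysis would have to invent one, and the p-value would follow from that choice.

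The descriptive rates could carry the aim, but three things are unstated: the level at which a woman counts as adherent, how women who withdraw are counted, and the period covered. A rate of adherence at baseline has no meaning, because no session has been assigned when the baseline assessments are made.

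What is at stake is the feasibility figure. The Future Plans section intends to pool these data with those of a similar pilot study to support a larger trial, so an ill-defined adherence figure would be carried forward.

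**Working it through.** **1. The plan's own figure.** Aim 2 has no figure of its own; the only stated size is 40 per arm, for the fatigue ANCOVA (Sample size Considerations).
- Pooled SD = √((9.35² + 9.42²)/2) = 9.385.
- Residual SD = 9.385 × √(1 − 0.64²) = 7.211.
- Difference = 42.53 − 37.12 = 5.41.
- n per arm = 2 × (1.960 + 1.282)² × 7.211² / 5.41² = 37.3, so 38.
- At 40 per arm the noncentral F (1 and 77 df) gives 91.2% power.

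The stated 40 per arm and 90% power are reproduced. Only the 40 is carried forward.

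**2. Where an adherence value exists.**

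| Item | Exercise arm | Control arm |
|---|---|---|
| Assigned sessions (Arm 1, Arm 2) | 15 minutes on each treatment day | none |
| Exercise log | described under Arm 1 | not mentioned |
| What the logs record (Study retention and adherence) | Pedlar time | no Pedlar assigned |
| Activity recall (Table 1) | screening only | screening only |

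No activity measure after screening could stand in for control adherence.

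**3. How far the p-value depends on the control score.** The plan does not say which form of binomial test is meant; I use Fisher's exact test, two-sided, at the plan's 0.05. Both control scores are assumptions. With 40 per arm and one empty cell, p = 2 × C(40,k)/C(80,k), where k is the count in the opposite cell.

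*Controls scored 0/40, since they do no Pedlar sessions:*
- 5/40 adherent: 2 × 658,008/24,040,016 = 0.055.
- 6/40 (15%): 2 × 3,838,380/300,500,200 = 0.026.
- 24/40: 7.7 × 10⁻¹⁰. 32/40: 7.0 × 10⁻¹⁵.

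*Controls scored 40/40, for keeping their usual habits:*
- 34/40 adherent (85%) leaves k = 6 non-adherent: p = 0.026, now favouring control.
- 36/40 (90%) leaves k = 4: p = 0.12.

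So 15% adherence can be a significant success and 85% a significant failure, depending on a score that is not defined.

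**4. What the exercise arm alone gives.** Clopper-Pearson 95% limits for x/n are the 2.5% point of Beta(x, n − x + 1) and the 97.5% point of Beta(x + 1, n − x). The rates are assumed, because the documents give none.
- 24/40 = 60% (43% to 75%).
- 32/40 = 80% (64% to 91%).
- 36/40 = 90% (76% to 97%).

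**5. Window and denominator.** Five treatments a week for 4 weeks is 20 sessions by T1. Fractionation is left to the treating physician, so the course may end before or after T1. Suppose a woman prescribed 25 treatments (assumed) exercises at 16 of the first 20 and at none afterwards.
- Rate to T1: 16/20 = 80%.
- Rate over the scheduled course: 16/25 = 64%.
- If her radiotherapy also stopped after 20 treatments, delivered sessions would give 16/20 = 80% and scheduled sessions 64%.

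The choice of scheduled or delivered sessions therefore matters for the same reason as the window.

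**6. Women without usable logs.** If there were 10 (assumed), 24 adherent women would be 24/30 = 80% (61% to 92%) of those with logs, but 24/40 = 60% of those randomized. This shows the direction of the effect; the documents give no reason to expect that many.

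**The case against.** The strongest reply is that little is at risk. Aim 2 is a pilot aim with no hypothesis, success threshold or go/no-go rule, and end-of-intervention rates are already promised. That stands: a reader might infer that the plan cannot answer Aim 2 at all, but those rates can answer it once defined. The fault lies in the test and the missing definitions.

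A reader might also conclude that the test would be significant for anything from 15% to 100% adherence. That holds only if controls are scored 0/40. Controls do have an instruction, to carry on as usual, and scoring them on it reverses the direction. The documents support the statement that the control value is undefined; they do not support that range.

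A further tempting reading is that lost logs would badly inflate the figure. The Study Design section says that every session is supervised at the radiotherapy facility, and a research assistant collects the logs. A missing entry most naturally means a session not done. A rule for withdrawals is still needed, but the risk is modest.

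The baseline adherence rate may be loose drafting. The last Aim 2 sentence limits the baseline-to-end comparison to acceptability, so the earlier phrase may simply pool the two. The window can also be partly inferred, since exercise is tied to each treatment; however, the change-score definition treats week 4 as the end of radiotherapy, whereas Study Design places T1 within the course.

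Finally, the contents of the appendices are not shown, and a form could define acceptability for both arms. It could hardly make adherence to Pedlar sessions meaningful for women assigned none. If retention or visit completion was meant, which both arms have, the text does not say so.

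**Conclusion.** The point holds, for Aim 2 only. The planned between-arm adherence test has no control value in the visible text. With 40 per arm its result can run from a significant difference at 15% adherence to a significant difference the other way at 85%, according to which of two assumed control scores is used. Neither result measures completion of the exercise. I am confident of the narrow statement that the visible text defines no control-arm adherence. The adherence rates, the 25-treatment course and the count of women without logs are illustrations, not findings.

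The fatigue and biomarker analyses and the sample size do not depend on any of this. The change should be made, but it does not threaten the trial's main result.

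**What to change.** Delete the between-arm adherence test and the baseline adherence rate, and put in their place:

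- **Per-woman rate.** For each woman randomized to exercise: 15-minute sessions completed, divided by radiotherapy sessions scheduled in her prescribed course. Show delivered sessions as a secondary denominator.
- **Summary.** The distribution of this rate, and the proportion of all women randomized to exercise who reach a level fixed before enrolment starts, with an exact 95% confidence interval. The team must set the level, since the documents give none.
- **Missing entries and withdrawals.** Because sessions are supervised on site, count a session with no log entry as not done. Keep women who withdraw in the denominator. Show the evaluable-only figure as a sensitivity analysis.
- **Window.** The whole course as the main window, with the window to T1 beside it. Reconcile the passages that place week 4 within the course and at its end.
- **Between-arm comparison.** If one is wanted, use something defined in both arms, such as retention or visit completion, and label it so.
- **Acceptability.** Limit acceptability of the exercise to the exercise arm unless an appendix form defines it for both arms.

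Cost: one between-arm p-value is lost. Lost logs may understate adherence; the sensitivity analysis shows by how much. Scheduled treatment dates must be taken from the radiotherapy record, because the treatment summary is marked at T2 only and may be missing for women lost before then. No new patient assessment is needed, and the sample size stays as it is.

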All participants in the study undergo RT as scheduled by their physician. The exercise intervention does not interfere with dose or timeline of RT. No specific requirements are made herein regarding prone or supine positioning, utilization of standard fractionation or hypofractionation, use of cardiac blocking or for utilization or omission of boost phase of radiation. These treatment decisions are completely at the discretion of the treating radiation oncologist. Adherence to the exercise intervention is achieved by offering participants flexibility in scheduling daily exercise, either before or after radiation treatment. Adherence is recorded in daily participation logs. Logs document participant identification, date, and length of time utilizing the Pedlar device. Participant retention efforts include a \$20 gift card incentive at baseline and one follow-up visit.

Assessments

Three assessments: at baseline, at 4-weeks into radiation course and at 4-week follow-up visit, will be assessed (see Table 1 below).

Table 1: Baseline and Follow-up Assessments

Assessment	Screening	Baseline (T0)	4 weeks (T1)	Follow-up visit (T2)
Eligibility (Appendix A)	X			
Informed Consent (Appendix B)	X			
Demographics (Appendix C)	X			
Medical history (Appendix C)	X			
Medications (from MD Consultation Note)	X			
Cancer and Treatment Summary (Appendix D)	X			
Performance Status	X			
Physical activity readiness questionnaire (Appendix C)	X			
Physical activity recall questionnaire (Appendix E)	X			
Blood tests for hematology (Appendix F)		X		
Vital signs and anthropometrics (Appendix G)		X	X	X
FACIT-Fatigue (in Appendix C)		X	X	X
FACT-B HRQOL (in Appendix C)		X	X	X
Inflammation biomarkers (Appendix F)		X	X	X
Adverse events assessments			X	X
Radiation Treatment Summary (by Treating MD)				X

Outcomes

Primary outcomes

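### Aim 2 tests acceptability from baseline to end of intervention and between arms, but no woman has used the programme at baseline, controls never receive it, and the main text names no acceptability measure

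*Combined protocol and SAP*

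**What the plan says.** The second of the three Specific Aims is "to provide pilot data on the acceptability and adherence of the exercise intervention on women receiving treatment". The Statistical analysis section gives this aim three analyses:

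- Rates at two times: "For Aim 2, we will report rates of acceptability and adherence at baseline and end of intervention".
- A comparison between arms: "We will use the binomial test to compare acceptance and adherence rates between the two intervention arms".
- A paired comparison over time: "Baseline and end of intervention acceptability levels evaluated using the Wilcoxon sign-rank test or McNemar's test", with a generalized McNemar test as a further option.

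The Randomization section fixes the order of events: "After completing baseline assessments, eligible participants will be assigned to study arm by a study coordinator". Under Intervention, the control arm gets no device and no sessions; those women are asked to carry on as they are.

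On measurement, the Abstract states "The outcome variables are CRF, biomarkers of inflammation, and health-related quality of life". The Outcomes section covers fatigue, the inflammation markers and quality of life. Table 1 lists what is done at screening, baseline (T0), 4 weeks (T1) and the follow-up visit (T2). For the other half of Aim 2 there is a source: "Adherence is recorded in daily participation logs".

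**The concern.** A paired test needs the same quantity measured twice in the same woman. Here the first measurement falls before anyone has tried the programme, so the natural meaning of acceptability, how women found it, is not available at that time. A between-arm test needs the quantity in both arms, and one arm never meets the programme. A reader also cannot find, in the main text, what would be asked or when.

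What is at stake is the feasibility evidence. The Future Plans section intends these data to support a larger trial. If an item were improvised to feed the planned tests, the p-values would answer a different question from the one in Aim 2. If no item were given, women's ratings near the end of the exercise period could not be properly recovered later, and only the exercise logs would remain as indirect evidence.

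**Working it through.** The documents state no acceptability rate, threshold or power, so there is no planned figure to reproduce. The check is mainly a comparison of sections.

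**1. Is there a baseline value?** Under Randomization, baseline assessments come first and assignment second; device use can only follow assignment. Two meanings of acceptability at T0 remain possible.

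- *Anticipated acceptability.* A woman could be asked at T0 whether she expects to find the programme acceptable. No such item is described, and the paired test would then contrast an expectation with an experience.
- *Acceptance as agreeing to join.* Every randomized woman has agreed, so all baseline answers are yes. In the McNemar table the no-to-yes cell is then zero by construction. With b women answering no at the end, the exact two-sided p-value is 2 × 0.5^b (for b of 1 or more). It depends only on b and can point only towards decline:

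| End-of-intervention no (b), of 40 | Still accepting | p = 2 × 0.5^b |
|---|---|---|
| 5 | 35/40 = 87.5% | 0.0625 |
| 6 | 34/40 = 85% | 0.031 |
| 8 | 32/40 = 80% | 0.008 |

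So 80% acceptance would appear as a significant fall from a 100% that was fixed by consent. The p-value adds nothing to the end-of-intervention proportion. These counts are illustrative and assume that all 40 women respond.

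**2. Is there a control value?** Controls have no device and no prescribed sessions. They have no experience of the programme to rate, so the binomial comparison of acceptance has no second proportion with the same meaning.

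**3. Is there a measure?** Table 1 has 16 rows: eligibility, consent, demographics, medical history, medications, cancer and treatment summary, performance status, activity readiness, activity recall, hematology, vital signs and anthropometrics, FACIT-Fatigue, FACT-B, inflammation biomarkers, adverse events, and radiation treatment summary. None is an acceptability measure (0 of 16). The primary and secondary outcomes name none. The logs, as described under Study retention and adherence, hold an identifier, a date and minutes of use; that is adherence.

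**4. What would one end-of-intervention item deliver?** The exact (Clopper-Pearson) 95% interval for x of n runs from the 2.5% quantile of Beta(x, n − x + 1) to the 97.5% quantile of Beta(x + 1, n − x). With n = 40, the planned arm size:

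- x = 32 (80%): 0.644 to 0.909, or 64% to 91%.
- x = 28 (70%): 0.535 to 0.834.

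Both counts are examples, not expectations from the documents, and assume full response. They describe the precision of the replacement analysis, not the size of the defect.

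**The case against.** **Table 1 is not exhaustive.** The adherence logs have no row in it, yet they are plainly collected. Blood counts are to be taken at every draw although the hematology row is ticked at baseline only. A reader might infer from 0 of 16 rows that a site would collect no acceptability data. That does not follow. Appendix C holds several questionnaires and Appendix H is the exercise log; neither is in the supplied text, and either could carry an item. This objection stands, and it limits the measurement point to what the main text names. It does not help the paired or between-arm tests.

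**A baseline value is conceivable.** A reader might say that no baseline value can exist at all. That is too strong: willingness or expectation can be asked before assignment. What stands is that no such construct is stated and that it would differ from the later rating.

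**The aim is only a pilot aim, and acceptance could be read behaviourally.** Uptake, attendance and retention would give partial evidence without a new instrument. A reader might conclude that half of Aim 2 is unanswerable; the documents do not support that either, since the logs would give some indirect information. But the plan names acceptability separately from adherence and gives it a test of its own. Women may also attend supervised sessions tied to their radiotherapy visits without finding them acceptable.

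**Conclusion.** The concern holds for the analysis plan. The paired test of acceptability has no baseline value of the quantity that Aim 2 is about, and the between-arm test of acceptance has no control value. This rests on the order of events and the arm descriptions in the main text, and on reading acceptability as women's experience of the programme; under the agreed-to-join reading the paired test is uninformative for a different reason.

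The measurement point holds in a narrower form: acceptability is not defined, and the main text names no measure of it. Whether an appendix contains one cannot be settled from the supplied text.

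The effect is confined to the acceptability part of Aim 2. The primary fatigue comparison and the 40 women per arm are untouched. The change is worth making before enrolment because it is cheap then and cannot be made fully afterwards.

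**What to change.** 1. In the Aim 2 text of the Statistical analysis section, delete the baseline-to-end test of acceptability, the reporting of acceptability at baseline, and the between-arm test of acceptance.
2. Add a Table 1 row for one short self-completed acceptability item, exercise arm only, at a named existing visit. T1 is one candidate, since the Statistical analysis section equates week 4 with the end of radiation treatment. Fractionation and boost are left to the treating physician, so the protocol should say that the item refers to the exercise period up to that visit. If an appendix already contains a suitable item, confirm it and schedule it instead. A 5-point rating of satisfaction and willingness to repeat the programme is one possible format.
3. Fix the cut that counts as acceptable before enrolment. Report the proportion with an exact 95% confidence interval, and the number of exercise-arm women who did not answer.

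The cost is one extra questionnaire item at an existing visit, one table row, a few sentences of analysis text, and the loss of the planned acceptability p-values. No extra visits, staff or participants are needed.
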